10.2. North Star Ambulatory Assessment (NSAA)

NSAA will be performed prior to ataluren dosing on the first day of treatment (Visit 2), Week 28 (Visit 5), and Week 52 (Visit 7/ET). The NSAA consists of 17 activities. For each of the evaluations, the subject will be scored with a 0 (Unable to achieve independently), 1 (Modified method but achieves goal independent of physical assistance from another) or a 2 (Normal – no obvious modification of activity). The maximum score is 34; the sum of the responses to the 17 individual questions will be the total score. If fewer than 13 of the 17 activities are performed, the total score will be considered missing. If from 13 to 16 activities are performed, the total score will be calculated by multiplying the sum of the scores in the x activities that were performed by 17/x. If an activity cannot be performed due to disease progression/loss of ambulation, a score of zero will be assigned.

Recent updates to the NSAA have removed ‘Lifts Head’ from the total score. Although the results from all 17 items have been collected, a summary will be presented based on the 16 items without the result from ‘Lifts Head’. The results of these 16 items will be summed on an intra- subject basis to obtain the total score. The best total score is 32 and the worst is 0.

In addition, the logit score will be performed per a linear transformation of the NSAA score to a scale of 0 to 100 [Mayhew 2013] based on the following table. This table illustrates the transformation of the raw score to the linearized measurement on a scale of 0 to 100 via a logit transformation. For example, a male who scored 12 out of 32 on the NSAA (excluding his score on item12 – lifts head) can be calculated to have a linearized measurement of 42 out of 100.

Results from the 16-item NSAA subscale will be presented in Table 14.2.2.1 entitled *Summary of 16-item North Star Ambulatory Assessment Total Score by Visit* (Evaluable Population) and Table 14.2.2.2 entitled *Summary of 16-item North Star Ambulatory Assessment Logit Score by Visit* (Evaluable Population).

The results of the entire 17-item NSAA scale will be presented in Table 14.2.2.1.1 entitled *Summary of the North Star Ambulatory Assessment Total Score by Visit* (Evaluable Population).

The results of the 8-item NSAA subscale will be presented in Table 14.2.2.1.2 entitled *Summary of the 8-item North Star Ambulatory Assessment Subscale by Visit* (Evaluable Population). The maximum score on the 8-item subscale is 16. If any of the 8 items are not performed, the total score will be considered missing.

The results of the 3-item NSAA subscale will be presented in Table 14.2.2.1.3 entitled *Summary of the 3-item North Star Ambulatory Assessment Subscale by Visit* (Evaluable Population). The maximum score on the 3-item subscale is 6. If any of the 3 items are not performed, the total score will be considered missing.

The supportive listing will be Listing 16.2.6.2 entitled *North Star Ambulatory Assessment*. This listing will be sorted by subject number and relative day.

Raw score	Logit	Logit (transformed 0–100)
0	−5.11	0 ^a
1	−4.25	11
2	−3.63	17
3	−3.19	21
4	−2.83	24
5	−2.52	27
6	−2.24	30
7	−1.99	32
8	−1.74	34
9	−1.51	36
10	−1.29	38
11	−1.07	40
12	−0.85	42
13	−0.64	44
14	−0.44	46
15	−0.23	48
16	−0.03	50
17	0.17	52
18	0.37	53
19	0.57	55
20	0.77	57
21	0.98	59
22	1.19	61
23	1.42	63
24	1.65	65
25	1.91	67
26	2.19	70
27	2.50	73
28	2.87	76
29	3.29	80
30	3.82	85
31	4.54	91
32	5.50	100

10.3. Palatability Characteristics

The responses to the Ataluren Palatability Questionnaire will be summarized in Table 14.2.3 entitled *Summary of the Palatability Characteristics at Visit 3* for all subjects in the Evaluable Population. The Ataluren Palatability Questionnaire has three questions, one for the child and two for the parent/caregiver. The questions, along with the response choices are:

1. Child: How did the medicine taste?
Responses: Bad, Not Sure, Good

2. Parent / Caregiver: On the basis of reaction / facial expression of your child, do you think that the medication is pleasant?
Responses: Strongly Disagree, Disagree, Neither Agree nor Disagree, Agree, Strongly Agree

3. Parent / Caregiver: You sometimes have problems in giving the medication to your child because he/she refuses to take it or throws it up.
Responses: Strongly Disagree, Disagree, Neither Agree nor Disagree, Agree, Strongly Agree

The counts and percentages for each question and response will be summarized at Visit 3. The supportive listing will be Listing 16.2.6.3 entitled *Palatability Characteristics*. This listing will be sorted by subject number and question.

11. PHARMACOKINETICS

11.1. Plasma Concentration

Collection of blood for ataluren plasma concentration analysis is critical for evaluating the exposure / safety relationships and profile in this study. Sampling pre-dose and then at 1, 2, 4, 6, 8, and 10 hours post-dose on Days 1 (Visit 2) and 28 (Visit 3) will provide information about single-dose and steady-state after 28-days of administration of ataluren. Plasma concentrations that are below the lower limit of detection will be set to zero for the tabular summary of the plasma concentrations by time point. Missing plasma concentrations will be excluded from the summary of the plasma concentrations by time point. The plasma concentration results will be summarized using descriptive statistics and presented in Table 14.2.4 entitled *Summary of the Plasma Concentrations of Ataluren by Visit* (PK Population). Listing 16.2.6.4 entitled *Plasma Concentrations of Ataluren* will contain the individual subject-level data sorted by subject number and date of the venipuncture sample used in the determination. Plasma concentrations will be summarized by scheduled time point in the tabular summary and all figures. However, the actual sampling times and the planned time points will be displayed in the plasma concentration listing.

Observed values of plasma concentrations for ataluren will be summarized at each visit and time point by dose level in the PK population. The descriptive statistics (n, mean, SD, CV%, median, minimum, and maximum) will be provided. In addition, geometric mean, its 95% CI, and CV% will be presented.

Figure 14.2.1 entitled *Mean (\pm SD) Ataluren Plasma Concentration by Visit over Time – Linear Scale* (PK Population) will plot the mean ataluren plasma concentrations over time for each visit in a linear scale. Figure 14.2.1.1 entitled *Mean (\pm SD) Ataluren Plasma Concentration by Visit over Time – Semi-Logarithmic Scale* (PK Population) will plot the mean ataluren plasma concentrations over time for each visit using a semi-logarithmic scale.

Plots of the plasma concentrations by subject will be presented in both linear and semi- logarithmic scale in Figure 14.2.2 entitled *Ataluren Plasma Concentration by Subject and Visit over Time – Linear Scale* (PK Population) and Figure 14.2.2.1 entitled *Ataluren Plasma Concentration by Subject and Visit over Time – Semi-Logarithmic Scale* (PK Population).

11.2. Pharmacokinetic Analysis

PK parameters (AUC_{0-t} , AUC_{0-10} , C_{max} , $C_{trough@6h}$, t_{max} , $AR(AUC)$, $AR(C_{max})$) will be derived using actual sampling and dosing times. Concentrations below the limit of quantitation (LOQ) will be set to zero for the calculation of NCA parameters.

Parameters	Definition
AUC_{0-10}	Area under the plasma concentration time curve from time zero to the time of last quantifiable concentration (C_{trough}) prior to the midday dose 6 hours after the morning dose using the linear trapezoidal rule during the ascending portion of the

Parameters	Definition
	curve. For the purpose of calculating AUC, when two consecutive BLQ plasma concentrations are encountered after t_{max} , these and all subsequent values will be excluded from the analysis. If missing values occur between two quantifiable concentrations, they will be excluded from the analysis.
AUC ₀₋₁₀	Area under the plasma concentration time curve from time zero up to 10 hours after the morning dosing using the linear trapezoidal rule during the ascending portion of the curve and the log-trapezoidal rule during the descending portion of the curve. For the purpose of calculating AUC, when two consecutive BLQ plasma concentrations are encountered after t_{max} , these and all subsequent values will be excluded from the analysis. If missing values occur between two quantifiable concentrations, they will be excluded from the analysis.
C _{max}	Maximum observed plasma concentration prior to the midday dose 6 hours after the morning dose. If multiple maxima occurred at equal concentrations, the first temporal value will be taken.
C _{trough@6h}	Concentration at the end of the first (morning) dosage interval (prior to the midday dose 6 hours after the morning dose)
t _{max}	Time of maximum observed plasma concentration prior to the midday dose 6 hours after the morning dose. If multiple maxima occurred at equal concentrations, the first temporal value will be taken.

The accumulation ratio on Day 28 will be calculated as follows:

Parameter	Description
AR(AUC)	$AR(AUC) = (AUC_{0-t}) \text{ on Day28} / (AUC_{0-t}) \text{ on Day 1}$
AR(C _{max})	$AR(C_{max}) = (C_{max}) \text{ on Day28} / (C_{max}) \text{ on Day 1}$

Note that Section 11.6 of the protocol also calls for the following PK parameters to be calculated:

λ_z The terminal rate constant

$t_{1/2}$ The terminal half-life, calculated as $\ln(2) / \lambda_z$

However, the dosing intervals, as planned by the protocol, will not allow for the calculation of these parameters.

PK parameters will be summarized with descriptive statistics on Day 1 and 28 (e.g., n, arithmetic mean, standard deviation, arithmetic CV %, median, minimum, and maximum, geometric mean, and geometric CV%). The analysis will be performed with a fully validated version of Phoenix WinNonlin V6.3. The individual pharmacokinetic parameters will be summarized using descriptive statistics and presented in the PK population in Table 14.2.5 entitled *Summary of the Ataluren Pharmacokinetics by Visit* (PK Population). Listing 16.2.6.5 entitled *Ataluren Pharmacokinetic Results* will contain the individual subject-level data sorted by subject number and date of the venipuncture sample used in the determination.

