3.4. Secondary Endpoints

The secondary endpoints are:

- Pharmacokinetic parameters (t_{max} , $t_{1/2}$, C_{max} , $C_{trough@6h}$, AUC_{0-10}), CL/F, and V_c/F based on frequent blood sampling for PK on Days 1 and 28 of ataluren treatment. On each of these days, blood samples for ataluren concentration assessments will be collected immediately pre-dose and at specified time points following the morning, midday, and evening doses. Ataluren concentrations in plasma will be analyzed using a validated HPLC-MS/MS method.
- TFTs (time to walk/run 10 meters, time to climb 4 stairs, time to descend 4 stairs, and time to stand up from a supine position)
- NSAA
- Changes in body weight, height, and BMI
- Ataluren palatability characteristics as determined by a parent/caregiver questionnaire

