6.2.3. Schedule of Administration

As noted in [Table 1](#), 3 doses should be taken per day – the 1st dose in the morning, the 2nd dose during the middle of the day (midday), and the 3rd dose in the evening. Intervals for dosing should be ~6 hours (± 1 hour) between morning and midday doses, ~6 hours (± 1 hour) between midday and evening doses, and ~12 hours (± 1 hour) between evening doses and the morning dose on the next day.

Table 1: Suggested Daily Dosing Schedule

Dose Designation	Example Dosing Times
Morning	~7:00 AM – 0700 hours (± 1 hour)
	↑ ~6 hours ↓
Mid-day	~1:00 PM – 1300 hours (± 1 hour)
	↑ ~6 hours ↓
Evening	~7:00 PM – 1900 hours (± 1 hour)
	↑ ~12 hours ↓
Next Day Morning	7:00 AM – 0700 hours (± 1 hour)

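### SAP 11.2 lets BLQ values in the morning interval delete quantifiable 8 and 10 h samples from AUC0-10, because the exclusion rule does not restart at the midday dose

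*SAP*

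**What the plan says.** SAP 11.2 describes AUC0-10 as the area "from time zero up to 10 hours after the morning dosing using the linear trapezoidal rule" while concentrations rise and the log-trapezoidal rule while they fall. Samples are drawn pre-dose and at 1, 2, 4, 6, 8 and 10 h (SAP 11.1). Protocol 6.2.3 puts the second dose inside that window: "Intervals for dosing should be ~6 hours (± 1 hour) between morning and midday doses". The SAP also works from a midday dose at 6 h, since tmax is the "Time of maximum observed plasma concentration prior to the midday dose 6 hours after the morning dose". The 8 and 10 h samples therefore normally measure the second dose.

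The AUC0-10 row carries two handling rules. After two consecutive BLQ values following tmax, "these and all subsequent values will be excluded from the analysis. If missing values occur between two quantifiable concentrations", the missing values are left out too. The same two sentences stand in the row for the area that ends before midday (its printed label reads AUC0-10, but its text is that of AUC0-t). Neither rule mentions the midday dose.

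The introduction to SAP 11.2 sets BLQ concentrations to zero for the non-compartmental parameters and uses actual sampling and dosing times. Protocol 11.6 has the set-to-zero rule but not the exclusion rule.

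**The concern.** Dropping everything after two consecutive BLQ values makes sense when one dose is washing out, because later readings are then likely to be noise. It does not make sense when a new dose has been given in between. As written, BLQ values at 2 and 4 h, or at 4 and 6 h, remove the 8 and 10 h values however high they are. A BLQ pair at 6 and 8 h removes the 10 h value.

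The tie rule adds a further case. If no Day 1 morning value is quantifiable, all are zero and the first is taken as the maximum. tmax can then be read as the pre-dose sample, and the 1 and 2 h values trigger exclusion of the whole profile.

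AUC0-10 is a named secondary endpoint (Protocol 3.4) and the only non-compartmental parameter in SAP 11.2 that uses the 8 and 10 h samples. With about 12 boys, one badly truncated value would move the mean and CV% in Table 14.2.5, and no flag is planned there.

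**Working it through.** The documents give no AUC0-10 value, LOQ or absorption rate, so there is no figure of the plan's own to reproduce. The rule is first applied literally, then its likelihood is gauged under stated assumptions.

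**1. The rule on a constructed profile.** Take concentrations 0, 10, 8, BLQ, BLQ, 10, 6 at 0, 1, 2, 4, 6, 8, 10 h. Rising segments, and segments that touch zero, are linear; falling segments are logarithmic.
- 0-1 h: (0 + 10)/2 = 5.00
- 1-2 h: (10 − 8)/ln(10/8) = 8.96
- 2-4 h, BLQ = 0: 2 × (8 + 0)/2 = 8.00
- 4-6 h: 0
- 6-8 h: 2 × (0 + 10)/2 = 10.00
- 8-10 h: 2 × (10 − 6)/ln(10/6) = 15.66

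| Handling | AUC0-10 |
|---|---|
| SAP rule as written (only 0-2 h survives) | 5.00 + 8.96 = 14.0 |
| Exclusion confined to each interval, second interval starting from zero at 6 h | 13.96 + 10.00 + 15.66 = 39.6 |
| All BLQ values set to zero, no exclusion | 47.6 |

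The post-midday area deleted is 25.7, which is 65% of 39.6. Against 47.6 the SAP rule loses (47.62 − 13.96)/47.62 = 71%.

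**2. Likelihood.** Protocol 14.1.2 reports, for three patients under 6 years at the same dose level, mean AUC0-24 of 279.3 h·µg/mL and mean Cmax of 28.2 µg/mL. As an illustration:
- mean concentration = 279.3/24 = 11.6 µg/mL
- CL/F = 40/279.3 = 0.143 L/h/kg
- V/F = 20/28.2 = 0.709 L/kg, assuming Cmax follows the 20 mg/kg dose
- half-life = ln 2 × 0.709/0.143 = about 3.4 h

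A one-compartment oral model with this CL/F, half-life 3.4 h, assumed ka 1.5/h and equal doses at 0 and 6 h gives Day 1 values of 0, 9.76, 10.14, 7.25, 4.85, 13.36 and 9.39 µg/mL. For the 4 h value to be BLQ at an assumed LOQ of 0.01 to 1 µg/mL, morning absorption would have to fall below 0.01/7.25 = 0.14% to 1/7.25 = 14% of normal. If the dose were fully absorbed, the half-life would have to be below about 0.2 to 0.54 h (ka 3/h). Over assumed half-lives of 1.5-6 h and ka 0.7-2.5/h, the 4 and 6 h values stay above about 29% and 11% of the morning peak. So the trigger needs a morning dose that is essentially lost, or extremely fast clearance.

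**3. What rests on the 8 and 10 h values.** With both doses normally absorbed (assumed half-life 1-6 h, ka 0.7-2.5/h), the 6-10 h part is 38-53% of the trapezoidal AUC0-10. In those profiles the rule does not fire, so this is not an expected loss. Where the morning dose is lost, the midday dose is most or all of the area, and the proportion lost is larger, as in step 1.

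**4. Missing 6 h sample.** Using the Day 1 profile in step 2:
- All samples: 4.88 + 9.95 + 17.23 + 11.94 + 18.21 + 22.52 = 84.7
- Without 6 h, the 4-8 h segment is 4 × (7.25 + 13.36)/2 = 41.22 in place of 11.94 + 18.21 = 30.15, total 95.8
- Ratio 95.8/84.7 = 1.13
- Exact model area: 93.4

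The full grid is therefore 9% low and the profile without the 6 h sample 3% high. Over half-life 1.5-6 h and ka 0.7-2.5/h on Day 1, the value without the sample is 9-19% above the value with it. Against the exact area, the full grid reads −22% to −4% and the profile without the sample −7% to +5%. The latter is closer at every Day 1 grid point, and at about 98% of points at steady state.

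**The case against.** The strongest objection is that the BLQ rule will hardly ever fire. Exposures in Protocol 14.1.2 are far above any plausible LOQ. A partly vomited dose lowers the curve without making it decline faster, and on Day 28 carry-over from earlier doses works against BLQ values. This stands, and it limits the point to a rare profile. It does not make the rule right. Vomiting was among the adverse events in the three patients under 6 years (Protocol 14.1.2), and the palatability questionnaire asks about the child throwing the medicine up, so a lost dose is foreseeable.

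A second objection is that the stakes are small and partly covered. AUC0-10 is descriptive, with no test or decision attached. Listing 16.2.6.4 and the by-subject figures would show the unused values. Protocol 11.6 plans a population PK analysis of the concentrations and refers to a separate PK analysis plan, not among the documents reviewed, which might deal with this. That also stands, but SAP 11.2 states the rule explicitly and would still need to agree with any such plan.

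A reader might go further and infer that skipping a missing 6 h sample biases AUC0-10, so that the value should be set to missing. The documents do not support that. The trapezoid on the full grid already under-reads, because nothing is drawn between 6 and 8 h, and under the assumptions in step 4 joining 4 h to 8 h usually lands nearer the true area. Setting the value to missing would discard it in a study of about 12 boys.

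**Conclusion.** The BLQ exclusion in the AUC0-10 row is wrong as written: it can remove valid post-midday concentrations on the strength of morning values. When it fires, the understatement is severe (14.0 against 39.6 or 47.6 in the constructed profile, and the whole area if the morning dose leaves nothing quantifiable). It should be uncommon, and only AUC0-10 is damaged by losing the 8 and 10 h values. The plan's text does not support a reading that midday exposure is routinely deleted.

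For a missing 6 h sample, the finding is one of comparability only: such a profile sits on a different scale, about 9-19% higher on Day 1 than with the sample. That range rests on an assumed one-compartment model with half-life 1.5-6 h and ka 0.7-2.5/h. How often either situation will arise cannot be read from the documents.

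**What to change.** In the AUC0-10 row of SAP 11.2, state that the two-consecutive-BLQ exclusion applies separately within each dosing interval (morning dose to the actual midday-dose time, and midday dose to 10 h), so that BLQ values before the midday dose never remove values after it. Add that BLQ values are otherwise set to zero, as the section already says, and that this includes the last pre-midday sample as the starting point of the second interval. Without that anchor the trapezoid in step 1 would join 2 h to 8 h and add 6 × (8 + 10)/2 = 54.0, giving 13.96 + 54.0 + 15.66 = 83.6. Check the label of the row that ends before midday, so that it is clear which row is amended.

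For a missing 6 h sample, keep the calculation and flag the profile in Listing 16.2.6.5.

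The cost is a sentence or two of SAP text and minor programming. No blood sample is added and no boy leaves the summary.

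The change does not cure the under-read caused by having no sample between 6 and 8 h, and is not meant to.

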8.2.11. Pharmacokinetic Assessment

During PK assessment on Days 1 and 28, patients will remain in the clinic until all blood draws are complete. On Days 1 and 28, blood samples for PK assessment will be drawn pre-dose and 1 (± 15 min), 2 (± 15 min), 4 (± 30 min), 6 (± 30 min), 8 (± 30 min), and 10 (± 30 min) hours post-dose. These samples will be sent to a central bioanalytical laboratory for analysis of ataluren levels. Please refer to the study manual for instructions regarding the collection, processing and shipment of all PK samples to the bioanalytical laboratory.

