11.6. Pharmacokinetic Parameters

PK parameters of ataluren on Day 1 and 28 will be derived using non-compartmental analysis (NCA) methods. The PK parameters of ataluren listed below will be derived following the morning dose on Day 1 and 28 using NCA methods.

Parameters	Definition
AUC _{0-t}	Area under the plasma concentration time curve from time zero to the time of last quantifiable concentration (C _{trough}) using the linear trapezoidal rule during the ascending portion of the curve and the log-trapezoidal rule during the descending portion of the curve
AUC ₀₋₁₀	Area under the plasma concentration time curve from time zero up to 10 hours after the morning dosing using the linear trapezoidal rule during the ascending portion of the curve and the log-trapezoidal rule during the descending portion of the curve
C _{max}	Maximum observed plasma concentration
C _{trough@6h}	Concentration at the end of the first (morning) dosage interval
t _{max}	Time of maximum observed plasma concentration
λ _z	Terminal rate constant
t _{1/2}	Terminal half-life, calculated as ln(2) / λ _z

The accumulation ratio on Day 28 will be calculated as follows:

Parameter	Description
AR(AUC)	$AR(AUC) = (AUC_{0-t})_{Day28} / (AUC_{0-t})_{Day 1}$
AR(C _{max})	$AR(C_{max}) = (C_{max})_{Day28} / (C_{max})_{Day 1}$

Individual PK parameters will be derived using actual sampling and dosing times. Concentrations below the limit of quantitation (LOQ) will be set to zero for the calculation of NCA parameters. PK parameters will be summarized with descriptive statistics on Day 1 and 28 (eg, n, arithmetic mean, standard deviation, standard error, median, minimum, and maximum, CV% mean, geometric mean, and CV% geometric mean). The analysis will be performed with a fully validated version of Phoenix WinNonlin V6.3.

In addition, a popPK analysis will be performed by simultaneously assessing concentrations on Days 1 and 28 in order to explore the potential time-dependency of ataluren and derive the following additional PK parameters.

Parameter	Description
ka	Rate constant of absorption
CL/F	Apparent clearance
CLd/F	Apparent distribution clearance
Vc/F	Apparent volume of distribution
Vp/F	Apparent peripheral volume of distribution

The above PopPK model will be used to simulate rich concentration-time profiles and derive the area under the curve over 24 hours (AUC_{0-24}).

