Twenty-four hour blood sampling for ataluren PK assessments was performed on Day 28 of each cycle; the data from Cycle 2, in which a dose of 10, 10, 20 mg/kg was administered, are of particular relevance to the proposed study. Ataluren plasma concentrations in the 3 patients < 6 years old were comparable to ataluren plasma concentrations in the 8 patients ≥ 6 years old who participated in the MMA study. Mean AUC_{0-24h} was 279.3 h $\cdot\mu$ g/mL and 358.4 h $\cdot\mu$ g/mL for patients < 6 and ≥ 6 years old, respectively, on Day 28 of Cycle 2. Mean C_{max} was 28.2 μ g/mL

and 29.9 µg/mL for patients <6 and ≥6 years old, respectively, on Day 28 of Cycle 2 (10, 10, 20 mg/kg). These data suggest similar ataluren PK profiles in patients <6 and ≥6 years old.

In Phase 2 clinical studies, ataluren has demonstrated comparable PD activity and safety, as well as PK profiles similar to adult patients, in children >6 years old with CF [Clancy 2006, Kerem 2008, Sermet-Gaudelus 2010, Wilschanski 2011]. The drug has also shown PD activity and was generally well-tolerated at the dose used in that study and a higher dose level in children with DMD [Finkel 2013].

During study conduct, patients will be monitored closely for adverse clinical and laboratory events. This protocol clearly defines the actions to be taken if AEs occur. Procedures have been established for defining AEs, eliciting AE information, recording AEs, evaluating the relationship of AEs to the study drug, grading the severity of AEs, following up on unresolved AEs, and reporting AEs. These procedures are fully detailed in Section 9. Additional risk/benefit information that becomes available during the conduct of the study will be provided to each investigational site as a “letter to the Investigator” or safety alert. In addition, pain and discomfort will be prevented as much as possible, and investigations will be limited to a minimum necessary to provide meaningful data and performed using size/age appropriate material and devices.

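### AUC0-10 is one NCA trapezoid across the midday dose with no sample until nominally 2 h after that dose; it will probably read low if absorption is prompt, and the plan neither says so nor shows a model-based value beside it

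*SAP*

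**What the plan says.** Protocol 3.4 lists AUC0-10 among the secondary PK endpoints, "based on frequent blood sampling for PK on Days 1 and 28 of ataluren treatment". SAP 11.2 defines it as "Area under the plasma concentration time curve from time zero up to 10 hours after the morning dosing using the linear trapezoidal rule"; the full rule is "using the linear trapezoidal rule during the ascending portion of the curve and the log-trapezoidal rule during the descending portion of the curve". It states no break at the midday dose and no limitation.

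Protocol 8.2.11 places samples pre-dose and at 1, 2 and 4 h, then "6 (± 30 min), 8 (± 30 min), and 10 (± 30 min) hours post-dose". Protocol 6.2.3 sets the second dose inside that window: "Intervals for dosing should be ~6 hours (± 1 hour) between morning and midday doses". SAP 11.2 takes Ctrough@6h before the midday dose, so the 6 h sample belongs to the morning interval. Protocol 3.4 and SAP 3.4.2 speak of samples after the midday and evening doses, but the only scheduled times after the midday dose are 8 and 10 h.

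SAP 11.2 restricts Cmax, tmax and Ctrough@6h to the time before the midday dose. It also drops the terminal rate constant and half-life because the dosing intervals do not allow them.

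Protocol 11.6 adds a population PK analysis: "The above PopPK model will be used to simulate rich concentration-time profiles and derive the area under the curve over 24 hours". SAP 11.2 and Table 14.2.5 carry no model-based exposure, and AUC0-10 is the only parameter there that spans two doses.

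**The concern.** The two doses inside AUC0-10 are sampled unequally. The morning dose has samples at 1, 2, 4 and 6 h. The midday dose has samples only at 2 and 4 h after it. Between 6 and 8 h the calculation draws one straight line from a trough to a value 2 h after a dose. If drug is absorbed promptly, the true curve lies above that line and the area between is lost. The loss depends on each boy's absorption speed, so it would also add spread between boys.

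At stake is the reading of Table 14.2.5. AUC0-10 would stand there without a caveat as the only multi-dose exposure figure for this age group. The SAP recognises the constraint of the dosing interval for its other NCA parameters but not for this one.

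**Working it through.** The documents state no expected AUC0-10, bias, tmax, lag or half-life, so there is no figure to reproduce. The check is a simulation under stated assumptions.

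**Inputs from the documents.** Samples at 0, 1, 2, 4, 6, 8, 10 h (Protocol 8.2.11); midday dose at about 6 h, equal to the morning dose (Protocol 6.2.1, 6.2.3); 6 h sample before that dose, linear-up/log-down rule (SAP 11.2).

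**Assumed.** One compartment, first-order absorption after lag L, no carry-over from earlier doses; half-life 2, 3, 4, 6 h; ka 0.8, 1.5, 3 per h (12 combinations); L = 0 to 1 h.

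**Formulas.** k = ln 2 / half-life. C(t) = f(t − L) + f(t − 6 − L), with f(u) = 10·ka/(ka − k)·(e^(−k·u) − e^(−ka·u)) for u > 0, otherwise 0. Rising segment: Δt·(C1 + C2)/2. Falling segment: Δt·(C1 − C2)/ln(C1/C2). Bias = 100·(trapezoid / numerically integrated area − 1). The dose scale cancels.

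**One case in full: half-life 3 h, ka 1.5, L = 0.** k = 0.231; 10·1.5/(1.5 − 0.231) = 11.82. Concentrations at the seven times are 0, 6.745, 6.858, 4.662, 2.954, 8.720, 5.835.

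| Segment (h) | Trapezoid | True |
|---|---|---|
| 0–1 | 3.37 | 4.43 |
| 1–2 | 6.80 | 7.01 |
| 2–4 | 11.38 | 11.55 |
| 4–6 | 7.49 | 7.50 |
| 6–8 | 11.67 | 16.18 |
| 8–10 | 14.36 | 14.53 |
| Total | 55.07 | 61.20 |

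- AUC0-10: 55.07/61.20 − 1 = −10.0%.
- 0–6 h: 29.04/30.49 − 1 = −4.8%.
- 6–10 h: 26.03/30.71 − 1 = −15.2%.
- The 6–8 h segment accounts for 4.50 of the 6.13 shortfall, or 73%. The rest is mostly the first hour after the morning dose.

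**All 12 combinations, by lag (bias range).**

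| Lag (h) | AUC0-10 | 0–6 h part | 6–10 h part |
|---|---|---|---|
| 0 | −19.0 to −4.8% | −9.5 to −3.0% | −28.9 to −6.3% |
| 0.25 | −11.5 to −2.4% | −2.3 to −0.8% | −21.1 to −3.2% |
| 0.5 | −4.6 to −0.6% | −1.1 to +3.0% | −12.6 to −0.4% |
| 0.75 | −0.2 to +0.8% (positive in 9 of 12) | −2.5 to +2.7% | −3.4 to +2.3% |
| 1 | −2.7 to −0.3% | −11.0 to −5.2% | +3.3 to +6.8% |

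The lag decides the answer. At 1 h the straight line overstates the midday part, because concentrations are still falling for the first hour after that dose, and the net shortfall comes from the morning.

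**Tie to the protocol's own exposure figures.** Protocol 14.1.2 gives mean AUC0-24 279.3 h·µg/mL and Cmax 28.2 µg/mL for three patients under 6 years with another disease. Matching ka to these at half-lives of 1.5–4 h gives −7.9% to −16.7% on Day 1 and −7.6% to −13.9% on Day 28 with no lag, and −1.5% to −4.8% on Day 1 with a 0.5 h lag.

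**Timing windows.** The 2 h gap is nominal. With the midday dose at 6 ± 1 h and the 8 h sample ± 0.5 h it can run from 7.5 − 7 = 0.5 h to 8.5 − 5 = 3.5 h. With random sampling windows, the midday dose at 5.5–6.5 h, the 6 h sample just before it, half-life 3 h and tmax 1–3 h, every simulated profile was low with no lag (mean −5% to −14%). At a 0.5 h lag 89–99% were low (mean −1.6% to −5.7%).

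**What does not depend on the midday interval.** Cmax, tmax and Ctrough@6h stop before the midday dose. The accumulation ratios use Cmax and AUC0-t. I take AUC0-t to be the first row of the SAP 11.2 table, whose definition ends at the pre-midday trough, although the label shown there is AUC0-10.

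**The case against.** Four points can fairly be made against this.

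1. *The size and even the direction rest on an absorption lag that nobody has stated.* The product is a low-solubility drug given as a suspension or mixed with semi-solid food (Protocol 2.2.2, 6.1.4), so zero lag cannot be presumed. This stands. A reader might infer that AUC0-10 is always or systematically too low, or that the midday peak is necessarily cut off; the table above does not support that.
2. *Nothing planned turns on it.* A reader might infer that exposure would look falsely low beside older patients, since Protocol 14.1.2 reports for the earlier study that "Twenty-four hour blood sampling for ataluren PK assessments was performed on Day 28 of each cycle". But those figures are AUC0-24 and Cmax. No AUC0-10 is given for older patients and no such comparison is planned. AUC0-10 is summarised descriptively, in a study whose primary objective is safety. This stands too.
3. *The protocol already handles it.* It calls the sampling sparse, plans a popPK model and defers detail to a separate PK analysis plan that is not among the documents. This stands only in part. That plan may cover the point, but SAP 11.2 and Table 14.2.5 as written show AUC0-10 alone and without comment.
4. *A model-based value is no gold standard.* With no early sample after the midday dose, the model must carry absorption over from the morning. Protocol 11.6 notes that an earlier adult model needed clearance to change between those two doses. This stands as a reason not to replace the NCA endpoint outright, but not as a reason to leave it unaccompanied.

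**Conclusion.** The gap is documented: AUC0-10 spans two doses, and the second has no planned sample in its first 2 h (nominal). With prompt absorption the NCA value will be low, by roughly 5–19% with no lag and 1–5% with a 0.5 h lag. Near a 0.75 h lag the error is negligible and of either sign. Part of any shortfall is ordinary sparse-sampling error in the morning interval, so the midday gap is not the whole cause.

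The percentages are illustrative. They assume one compartment and constant clearance, whereas Protocol 11.6 mentions two compartments with time-dependent clearance. Over a wider assumed grid (tmax 0.5–4 h, half-life 1.5–6 h) the no-lag range is 3.4% to 28.4% low.

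This is a cheap improvement to the reporting of one secondary endpoint. It does not threaten the study's main conclusions.

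**What to change.** In SAP 11.2 and Table 14.2.5:

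- Keep the NCA AUC0-10 as specified.
- Report beside it each boy's AUC0-10 from his individual popPK fit, using actual dose and sampling times, a dense simulated profile and allowance for a morning-to-midday change in clearance. This is the model Protocol 11.6 already plans for AUC0-24.
- Footnote the NCA value as likely underestimated if absorption is prompt, because no sample is planned in the first 2 h after the midday dose. Do not call it a lower bound, since with some lags it is not one.
- Base statements about multi-dose exposure on the model-based values.

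The cost is SAP (or PK analysis plan) wording and one extra output, with no extra blood. The downside is that the added value depends on the model. An added 7 h sample is not a clean alternative: at half-life 3 h and tmax 1 h it moves the Day 1 bias from −13.8% to −6.8% with no lag, but from −5.4% to +2.9% with a 0.5 h lag, and it costs a further draw from small children.
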